The nutritional knowledge section evaluates patients' understanding of nutrient composition, dietary recommendations, and the relationship between nutrition and cancer treatment outcomes. The attitude section measures patients' perceptions and beliefs regarding the importance of nutrition in managing cancer-related symptoms and treatment side effects. The practice section assesses

actual dietary behaviors, including food choices, meal frequency, and adherence to nutritional recommendations.

Short-Term & Long-Term Clinical Outcomes

Short-term clinical outcomes will focus on early posthospitalization events within 30 days of admission, providing insights into the immediate impact of nutritional status on patient recovery and complications. These outcomes will include 30-day survival status, intensive care unit (ICU) admissions, length of stay, and total hospitalization costs, with a specific breakdown of nutrition-related expenses, such as enteral and parenteral nutrition. Additionally, changes in body weight within 30 days of hospitalization will be monitored as a key indicator of early nutritional deterioration. The incidence of complications, including infections, malnutrition, and drug-related adverse effects, will be systematically recorded to assess treatment-related risks. These measures provide critical data on the role of nutritional status in influencing short-term recovery, treatment complications, and overall resource utilization.

Long-term clinical outcomes will be assessed through regular survival tracking at each scheduled follow-up visit. Patient survival status will be documented to analyze survival trends over time and the potential impact of nutritional interventions on overall prognosis. The follow-up evaluations will categorize patients as alive and disease-free, alive with disease progression, or deceased, with the cause of death recorded.

Adverse Event Recording

Adverse events (AEs) will be systematically recorded and monitored throughout the study to ensure patient safety and data integrity. AEs are defined as any unfavorable or unintended medical occurrence, regardless of their direct relationship with nutritional interventions or treatment. These may include treatment-related complications, gastrointestinal distress, metabolic imbalances, infections, allergic reactions, or other unexpected health changes.

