At each follow-up visit, trained personnel will actively assess AEs by reviewing medical records and laboratory findings, while participants will be encouraged to self-report symptoms between visits. Serious adverse events (SAEs), including hospitalization, prolonged disability, or life-threatening conditions, will be reported following institutional and ethical guidelines.

All AEs and SAEs are classified by severity, duration, and potential causality, with standardized

procedures for data entry, review, and risk assessment. Necessary medical interventions or protocol adjustments will be implemented as needed. This structured monitoring system will increase patient safety, reduce risks, and provide insights into the impact of nutritional interventions on clinical outcomes.

Follow-up assessments and data collection timeline

Follow-up assessments will be conducted at predefined intervals to track longitudinal changes in nutritional status, clinical outcomes, and survival trends. In the first year, participants will be closely monitored at 1, 2, 3, 6, and 12 months to assess early nutritional changes and treatment-related complications. Afterward, annual follow-ups will continue for an additional four years or until death or loss to follow-up, with a focus on survival status and disease progression. In-person hospital visits will be prioritized for follow-up to ensure a comprehensive evaluation of nutritional status, clinical outcomes, and quality of life (**Table 1**). If in-person visits are not feasible, telephone follow-ups serve as an alternative. Research personnel will document each follow-up attempt, including the method of contact, date, and details of the interaction. To minimize loss to follow-up, participants missing scheduled visits were contacted up to three times via phone calls or text messages. If a participant remains unreachable after three attempts, they will be classified as lost to follow-up, and their last recorded assessment will be used for analysis. Any known reasons for withdrawal, relocation, or health deterioration will be documented to ensure data transparency and completeness.

Variable	SV	Folllow-up						
		1 st month	2 nd month	3 rd month	6 th month	12 th month	Annually follow-up for another 4 years	

Demographics & Clinical Data	√						
KPS Scoring	√	√	√	√	√	√	√
mPG-SGA	√	√	√	√	√	√	√
NRS2002	√	√	√	√	√	√	√
Standardized anthropometric measurements	√	√	√	√	√	√	√
SDSAT	√	√	√	√	√	√	√

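### Three failed contacts after one missed visit classify a participant as lost, with no route back and no vital-status check described, so unseen deaths may be censored as losses

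*Protocol*

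**What the plan says.** The rule is in the Protocol, Follow-up assessments and data collection timeline. In the first year "participants will be closely monitored at 1, 2, 3, 6, and 12 months"; after that, "annual follow-ups will continue for an additional four years or until death or loss to follow-up". In-person visits are preferred, but "If in-person visits are not feasible, telephone follow-ups serve as an alternative".

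For non-attenders, "participants missing scheduled visits were contacted up to three times via phone calls or text messages". The loss rule follows: "If a participant remains unreachable after three attempts, they will be classified as lost to follow-up". As to the data of such a participant, the Protocol adds that "their last recorded assessment will be used for analysis". Reasons such as withdrawal, relocation or worsening health are documented if they are known.

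Under Short-Term & Long-Term Clinical Outcomes, "Long-term clinical outcomes will be assessed through regular survival tracking at each scheduled follow-up visit". One of the outcome categories is "deceased, with the cause of death recorded".

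The Statistical analysis plan section names Kaplan-Meier, log-rank and Cox analyses for overall survival (OS) and progression-free survival (PFS). It also lists survival among the binary outcomes for logistic regression.

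**The concern.** Survival is found out through the scheduled visits, and the loss rule can end those visits. The rule can be triggered by any one scheduled visit, and the stated contact attempts are calls or texts to the participant. A patient who has died or is gravely ill cannot answer them. Nothing in the rule asks staff to establish whether an unreachable participant is alive before the status is assigned.

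A death that the site never hears of can go wrong in two ways. In the Kaplan-Meier and Cox analyses it becomes a censored observation. In the logistic analysis, use of the last recorded assessment can make it a survivor.

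The Introduction itself links malnutrition to morbidity and survival. The exposure is therefore a plausible cause of being unreachable, and censoring that depends on unrecorded death violates the assumption behind all three survival methods. The other planned devices do not repair this. Multiple imputation under its usual missing-at-random assumption does not recover such deaths, and the sensitivity analysis that excludes incomplete follow-up would drop these patients. Whatever the SAP says about censoring, it cannot restore a death that nobody looked for.

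**Working it through.** **1. The plan's own attrition figure.** The Sample size section cites 30% to 50% attrition from other cohorts and gives a target of about 1,538. Inputs: two-sided 0.05, 80% power, the symbol values 0.50 and 0.40, and 1:1 allocation (assumed).

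- Per group, unpooled: (0.50×0.50 + 0.40×0.60) × (1.960 + 0.842)² / 0.10² = 384.6; total 769.2.
- Divided by (1 − 0.50): 1,538.4, which matches. At 30% attrition the result is 1,099, which does not.

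The target therefore rests on losing half the cohort. (The rates given in words, 20% and 24%, contradict these symbols; that is a separate matter.) With vital status for all 1,538, 769 per group, power for 0.50 versus 0.40 would be 97.7%, against 79.7% with half lost.

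**2. Cumulative loss if loss is terminal.** Scheduled visits: 5 in the first year + 4 annual = 9. Let q be the probability, per visit, of missing it and being unreachable. The documents do not give q. Assuming independent misses and ignoring deaths, cumulative loss = 1 − (1 − q)⁹.

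| q | Cumulative loss |
|---|---|
| 2% | 16.6% |
| 3% | 24.0% |
| 3.9% | 30% |
| 5% | 37.0% |
| 7.4% | 50% |
| 10% | 61.3% |

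Writing q as m × a³ (m = visit missed, a = no answer per attempt, all independent) shows how far the result depends on the inputs:

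- m = 10%, a = 0.5: 10.7%
- m = 20%, a = 0.6: 32.8%
- m = 20%, a = 0.7: 47.2%

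**3. Hidden deaths, illustration only.** Assume true 5-year mortality of 50% (malnourished) and 40% (not), constant hazard ratio ln 0.50 / ln 0.60 = 1.36. Let a share f of deaths be censored at the time of death, with f constant over time. Apparent Kaplan-Meier mortality = 1 − (1 − mortality)^(1 − f). The apparent hazard ratio is 1.36 × (1 − f malnourished)/(1 − f other).

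| Share hidden: malnourished / other | Apparent mortality | Apparent hazard ratio |
|---|---|---|
| 1/3 / 1/3 | 37.0% vs 28.9% | 1.36 |
| 40% / 20% | 34.0% vs 33.5% | 1.02 |
| 20% / 40% | 42.6% vs 26.4% | 1.81 |

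If the hidden deaths count as survivors in a binary analysis, the 40% / 20% case gives 0.50 × 0.60 = 30% versus 0.40 × 0.80 = 32%, and the direction reverses.

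**The case against.** Several stronger readings are tempting, and the documents do not support them.

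- **That one unreachable visit permanently closes a participant out.** The end-point wording sits in the sentence on annual follow-up. Nothing cancels the remaining first-year visits after, say, an unreachable month 2, and re-entry is not forbidden. What stands is that no re-entry is provided for.
- **That deaths are recorded as losses.** Deaths that become known are coded as such, with cause. Staff review medical records for adverse events at each follow-up visit, ICU admission within 30 days is recorded, and a relative may answer the telephone. Only deaths that escape these routes are affected. None of the routes is stated as a check on an unreachable participant.
- **That the rule produces the 30% to 50% attrition.** The Protocol takes that range from cited cohorts. The per-visit rate needed to reach it is assumed, and plausible inputs give as little as 10.7%. The formula also keeps everyone at risk for nine visits, and its independence assumption sits badly with patients who are unreachable because they are dead or very ill.
- **That OS and PFS differences shrink.** With equal hidden shares the hazard ratio stays at 1.36 and only the absolute gap narrows. The near-null result needs an assumed 40% versus 20% split, and the opposite split exaggerates the difference.

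The target already allows for 50% loss. That protects precision; it does not protect against informative loss.

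**Conclusion.** The concern holds in a limited form. As written, the Protocol classifies a participant as lost after one missed visit and three failed contacts, makes loss an end point of annual follow-up, gives no route back, and describes no vital-status check. Deaths unknown to the site may be censored, or counted as survivors in the logistic analysis.

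That this censoring is informative is likely rather than shown: it rests on the premise that malnutrition predicts being too ill or dead to answer. The bias cannot be sized from the documents. Depending on the hidden share in each group, the illustrations run from an unchanged hazard ratio of 1.36 down to 1.02 or up to 1.81. The cumulative-loss figures likewise rest on an assumed per-visit rate, independent misses and terminal loss.

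The change is worth making because it is cheap, concerns the main long-term outcome, and cannot be made good at the analysis stage.

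**What to change.** Reword the follow-up section of the Protocol as follows.

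1. Three failed attempts make that visit missed. Contact is attempted again at every later scheduled visit unless consent is withdrawn.
2. Before loss is coded, existing staff check the hospital record for vital status and for the date of death or the date last known alive.
3. The same check is applied to all participants at the same time points. Searching for deaths only among the unreachable, while censoring the others at last contact, would itself bias mortality upward.
4. The censoring date is stated, and the last recorded assessment is not used as evidence of survival beyond its own date.

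A family-contact field would help, but the documents do not say that one is collected: the Informed Consent Process section says only that families receive study information. If it is added, it must be covered in the consent and reconciled with the Data Privacy & Confidentiality section, which rules out recording personal identifiers.

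The cost is protocol wording plus more contact attempts and record checks, by staff who already review records. Site records will still miss some deaths that occur elsewhere, so the problem is reduced rather than removed.

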The sample size for the NCOM study was determined on the basis of the impact of nutritional status on clinical outcomes in cancer patients, with a two-sided significance level (α) of 0.05 and 80% power ($1 - \beta = 0.80$) (von Elm *et al*, 2007; Arends *et al*, 2017). On the basis of previous studies on nutritional status and cancer outcomes, we assumed a baseline event rate of 20% ($P_1 = 0.50$) in the unexposed group and an expected rate of 24% ($P_2 = 0.40$) in the exposed group (Rasschaert *et al*, 2024). Given that longitudinal oncology cohort studies report attrition rates ranging from 30% to 50% over a multiyear follow-up period (Reeves *et al*, 2007; Schwedhelm *et al*, 2016), the final target sample size for this study was estimated to be approximately 1,538 participants.

Data collection

Data collection followed a standardized protocol across all participating hospitals to ensure consistency and accuracy. The baseline assessments will be conducted within 48 hours of hospital admission, and well-trained researchers will collect information on demographic and clinical data, nutritional status, laboratory biomarkers, quality of life, psychosocial factors, physical activity, sleep status, and knowledge, attitudes, and practices (KAPs). Follow-up assessments will be conducted at predefined intervals to track longitudinal changes in nutritional status and clinical outcomes.

To ensure data reliability, each hospital will designate 1 to 2 trained personnel to be responsible for questionnaires and clinical data recording. At the same time, a supervisor will be appointed to review the integrity of the data and coordinate follow-up work if necessary. All researcher personnel

must complete standardized training and pass competency assessments to ensure consistency in data collection and minimize variations.

Data management will be centralized through the Research Electronic Data Capture (REDCap) system, which ensures data security, accuracy, and accessibility(Harris *et al*, 2009). Standardized, validated measurement tools will be used at each site. Data entry will include built-in validation checks to identify missing values or inconsistencies, with routine audits and cross-site comparisons performed to maintain high data quality and study validity.

Data Content & Assessment Tools

Demographics & Clinical Data

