Secondary analyses will investigate associations between nutritional status and psychosocial factors (e.g., EORTC QLQ-C30, HADS, PSQI) via paired t tests, mixed-effects models, and correlation analyses (Spearman or Pearson, depending on distribution).

To minimize bias and confounding factors, propensity score matching (PSM) will balance baseline differences between exposure groups. Multiple imputation will handle missing data to prevent systematic bias, and sensitivity analyses will exclude cases with extreme values, incomplete follow-ups, or protocol deviations.

Subgroup analyses will stratify findings by cancer type, treatment modality, and nutritional status category. Interaction terms are included in regression models to identify potential effect modifications, with exploratory analyses conducted if unexpected patterns arise.

By integrating multivariate modeling, survival analysis, repeated measures approaches, and

missing data imputation, this study ensures robust, high-quality, evidence-based insights into the impact of nutritional status on clinical outcomes and survival in cancer patients.

Informed Consent Process

Participation in this study is voluntary, and individuals may withdraw at any time without affecting their medical care. Before enrollment, participants and their families will receive detailed study information, including their purpose, methodology, potential risks, and benefits. A written informed consent form must be signed, confirming their understanding and voluntary participation.

The informed consent process will be conducted by trained research personnel, ensuring that participants fully understand the study's objectives and procedures; are aware of their right to withdraw at any time without impacting their current or future medical treatment; and have the opportunity to ask questions and receive clarifications before signing.

To accommodate diverse literacy levels, consent materials will be provided in clear, accessible language, with verbal explanations when needed. The informed consent form included both English and Chinese versions (**Supplementary File 1**).

Data Privacy & Confidentiality

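### For visits after loss to follow-up, the protocol prescribes both the last recorded assessment and multiple imputation; outside time-to-event analyses the first rule biases results, and no precedence is stated

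*Protocol*

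**What the plan says.** **Protocol, Follow-up assessments and data collection timeline.** The rule applies once three contact attempts have failed. Of such patients the section says: "they will be classified as lost to follow-up, and their last recorded assessment will be used for analysis". It excepts no outcome and is not labelled a sensitivity analysis.

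**Protocol, Statistical analysis plan.** "Multiple imputation will handle missing data to prevent systematic bias, and sensitivity analyses will exclude cases with extreme values, incomplete follow-ups, or protocol deviations". The same section lists the analyses that would meet these data:
- under the primary outcome analysis, logistic regression for binary outcomes (survival is one of its examples) and linear regression for changes in BMI and weight;
- GEE for repeated nutritional status, biomarkers and quality of life;
- Kaplan-Meier and Cox models for OS and PFS;
- mixed-effects models among the secondary analyses.

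**Protocol, Sample size.** The planning premise is that "longitudinal oncology cohort studies report attrition rates ranging from 30% to 50% over a multiyear follow-up period".

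**Protocol, Introduction.** Nutritional status is expected to shift during treatment, and capturing that change is the stated reason for the cohort.

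**The concern.** A value missing after loss cannot be both fixed at the last recorded assessment and multiply imputed. The protocol does not say which rule governs, so two analysts could follow different sentences, both claim compliance and report different results.

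The choice matters because the two rules do not carry the same bias. Holding a patient at the last recorded state assumes that nothing changed afterwards, which is at odds with the protocol's own expectation of change. The follow-up section also names worsening health, alongside withdrawal and moving away, as a reason for loss to be documented, so loss related to illness is foreseen. The primary regression models are among the analyses exposed.

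**Working it through.** **1. What the follow-up rule does in each planned analysis**

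| Analysis | Effect of using the last recorded assessment |
|---|---|
| Kaplan-Meier, Cox | Can serve as the censoring date; standard, though censoring may still be informative |
| Logistic regression of survival | Patient lost while alive is counted as a survivor |
| Linear regression of change | Change stops at the last visit |
| GEE, mixed models | Last value is repeated at later visits |

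**2. The attrition built into the sample size**

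Inputs (Sample size section): "with a two-sided significance level (α) of 0.05 and 80% power"; rates 0.50 and 0.40 as given in symbols.
- n per group = (1.960 + 0.842)² × (0.50×0.50 + 0.40×0.60) / 0.10² = 384.6, so 769.2 in total.
- At 50% attrition: 769.2 / 0.50 = 1,538.4, which is the plan's 1,538. At 40% the result is 1,282 and at 30% it is 1,099.
- The rates given in words (20% and 24%) need 3,359 before any attrition, so they cannot produce 1,538. That discrepancy is a separate matter.

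Patients who could fall under the rule: 0.30 × 1,538 = 461 to 0.50 × 1,538 = 769.

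**3. Mean change over the whole follow-up**

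Assumptions: equal steps of change over the nine post-baseline visits (months 1, 2, 3, 6, 12 and four annual), a constant chance of loss per visit, and loss unrelated to outcome. With total loss D, the chance of staying from one visit to the next is q = (1 − D)^(1/9). The share of true change kept is (q + q² + … + q⁹) / 9 = q(1 − q⁹) / [9(1 − q)].
- D = 0.30: q = 0.9611, share = 0.82.
- D = 0.50: q = 0.9259, share = 0.69.

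**4. A 12-month difference**

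Assumptions: constant loss over 5 years, linear change, and all first-year loss placed at month 3.
- Lost by month 12: 1 − 0.7^0.2 = 6.9%; 1 − 0.5^0.2 = 12.9%.
- Shrinkage: 0.069 × (1 − 3/12) = 5%; 0.129 × 0.75 = 10%.

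**5. Logistic regression of survival with no true effect**

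Assumptions: 5-year mortality of 50% in both groups; independent exponential loss whose 5-year probability, ignoring death, is 30% in the unexposed and 50% in the exposed. Cumulative hazards are 0.693 for death and 0.357 or 0.693 for loss. The observed proportion with each event is its hazard over the sum, times (1 − e^−sum).

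| | Unexposed | Exposed | OR |
|---|---|---|---|
| Deaths observed | 0.693/1.050 × 0.65 = 42.9% | 0.5 × 0.75 = 37.5% | |
| Lost while alive | 0.357/1.050 × 0.65 = 22.1% | 0.5 × 0.75 = 37.5% | |
| Odds of death, lost counted as alive | 0.429/0.571 = 0.751 | 0.375/0.625 = 0.600 | 0.80 |
| Odds of death, lost excluded | 0.551/0.449 = 1.226 | 0.600/0.400 = 1.500 | 1.22 |

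With equal loss, the two columns coincide and both odds ratios are 1. Equal loss still shrinks a real effect: if a share m of deaths in each group goes unrecorded and is counted as survival, the risk difference is multiplied by 1 − m. At m = 0.30 a difference of 0.10 becomes 0.07, and at m = 0.50 it becomes 0.05.

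**The case against.** The strongest defence is that the follow-up sentence never mentions carrying values forward. For time-to-event outcomes its natural meaning is censoring at the last assessment, and under independent loss Kaplan-Meier and Cox estimates are then unbiased. This stands, and the point does not extend to those analyses. It does not rescue the logistic, linear, GEE or mixed-model analyses. A milder reading, that data up to the last assessment are simply retained, is possible, but the sentence does not say so. Nor can the matter be left to a separate SAP, because the protocol itself fixes both rules.

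A reader might also infer stronger claims that the documents do not support:
- **That the rule leaves nothing to impute.** It covers only patients who cannot be reached. Unavailable laboratory values, missed visits later resumed and incomplete questionnaires remain for imputation.
- **That excluding incomplete follow-up is a third conflicting rule.** It is labelled a sensitivity analysis and is meant to differ. A gap such as 0.80 against 1.22 would show that the result depends on the rule, though neither value recovers the null.
- **That excluding extreme values removes the most malnourished.** The protocol does not define extreme; it could mean laboratory or cost outliers.
- **That a 12-month difference shrinks by 22% to 38%.** This places all 30% to 50% of the loss at month 3 (0.30 × 0.75; 0.50 × 0.75), whereas the protocol gives that range for several years and states no timing.

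**Conclusion.** The conflict is real for visits after loss, reaches the primary analysis and should be resolved before any analysis. Its possible extent is up to about 461 to 769 of 1,538 patients. That range comes from other cohorts, and the protocol does not say whether it includes deaths, which are not loss to follow-up.

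The size of the bias depends on assumptions. Carrying forward keeps about 82% to 69% of the mean change over all visits and takes about 5% to 10% off a 12-month difference. The odds ratios of 0.80 and 1.22 apply only to logistic regression of survival and rest on an assumed loss of 30% versus 50% between exposure groups. The documents give those figures as a range across studies, not as a difference between groups.

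A reader might conclude that 30% to 50% of patients are frozen just before decline or death. That goes too far: withdrawal and moving away are also listed as reasons for loss, and what happens after loss is unknown.

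**What to change.** - In the follow-up section, restrict the sentence to time-to-event outcomes: censor at the last date known alive for OS and at the last disease assessment for PFS.
- Analyse long-term survival by time-to-event methods, not by logistic regression with lost patients counted as alive.
- In the Statistical analysis plan section, state that other outcomes after loss are handled by the planned multiple imputation or the mixed models already listed, with no imputation beyond death.
- Add a sensitivity analysis for data missing not at random, for example delta-adjusted imputation with worse values after loss, rather than relying on exclusion of incomplete follow-up.

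The cost is wording in two sections and a little more analysis work. No further data are needed and the sample size does not change. Inverse-probability-of-censoring weighting would be a reasonable extra but is a preference, and the sensitivity analysis on extreme values need not be removed.

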Upon enrollment, trained personnel will obtain informed consent and record demographic details, including sex, age, marital status, occupation, education, and socioeconomic status. Lifestyle factors such as smoking, alcohol, and tea consumption are documented, given their potential influence on nutritional status and cancer progression(Yuan *et al*, 2023). Medical history, including chronic conditions, previous diagnoses, medication use, and family history of malignancies, will also be recorded to assess genetic predispositions.

Cancer-specific data will be collected at baseline and updated at follow-ups to monitor disease progression and treatment response. This includes pathology-confirmed diagnosis, TNM staging at first diagnosis, and available molecular markers. The tumor burden will be reassessed at each visit, alongside major treatments (surgery, chemotherapy, radiotherapy, targeted therapy, and immunotherapy), with details on the type, duration, and response. Nutritional support, including enteral or parenteral nutrition in the preceding week, will be tracked to evaluate its impact on treatment outcomes.

Karnofsky Performance Status (KPS): The KPS evaluates a patient's ability to perform daily activities, the presence of physical discomfort, and overall performance status, providing a standardized measure of functional impairment(McNair *et al*, 2023).

Nutritional assessments

Nutritional assessments will be conducted via validated screening tools to evaluate nutritional status, risk factors, and dietary intake patterns. Two primary tools and standardized anthropometric

measurements will be employed to assess malnutrition risk and severity:

Subjective Global Assessment (mPG-SGA): The mPG-SGA scoring system consists of five sections: weight loss history, dietary intake changes, symptoms, activity and function levels, and age. Patients' nutritional status will be categorized on the basis of scores as normal (0–2 points), mild malnutrition (3–6 points), and moderate malnutrition (≥ 7 points)(Huo *et al*, 2023a). The version used in this study, mPG-SGAL11, is an adapted and validated version developed for Chinese cancer patients who that incorporates modifications on the basis of nationwide clinical feedback and statistical validation(Fu *et al*, 2022; Huo *et al*, 2023b).

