Nutrition support in and out of hospital Nutrition support	√	√	√	√	√	√	√
Laboratory biomarkers	√	√	√	√	√	√	√
EORTC QLQ-C30	√	√	√	√	√	√	√
HADS	√	√	√	√	√	√	√
PSQI	√	√	√	√	√	√	√
Leisure-time physical activity levels	√	√	√	√	√	√	√
KAP Questionnaire	√				√	√	√
Short-Term Clinical Outcome		√	√	√	√	√	√
Long-term clinical outcomes		√	√	√	√	√	√
Adverse Event Recording	√	√	√	√	√	√	√

299 **Table 1.** Follow-up schedule. SV: screening visit; KPS: Karnofsky Performance Status; mPG-SGA:
 300 Subjective Global Assessment; NRS-2002: Nutritional Risk Screening 2002; SDSAT: Simple Diet Self-
 301 Assessment Tool; EORTC QLQ-C30: European Organization for Research and Treatment of Cancer

Quality of Life Questionnaire C30; HADS: Hospital Anxiety and Depression Scale; PSQI: Pittsburgh Sleep Quality Index; KAP : Knowledge, Attitude, and Practice.

Statistical analysis plan

Baseline characteristics are summarized as the means \pm standard deviations (SDs) for normally distributed variables, medians with interquartile ranges (IQRs) for skewed data, and percentages for categorical variables. For group comparisons (e.g., normal vs. mild malnutrition vs. moderate malnutrition patients), independent t tests or Mann–Whitney U tests were used for continuous variables, and chi–square tests or Fisher’s exact tests were used for categorical data.

The primary outcome analysis will apply multivariate regression models, adjusting for age, sex, cancer stage, treatment modality, socioeconomic status, and baseline Karnofsky Performance Status (KPS). Logistic regression was used to assess binary outcomes (e.g., nutritional risk, survival), whereas linear regression was used to evaluate continuous variables (e.g., BMI changes, weight loss percentage). To account for repeated measures, generalized estimating equations (GEEs) model longitudinal variations in nutritional status, biomarkers, and quality of life.

For survival analysis, Kaplan–Meier curves were used to estimate overall survival (OS) and progression-free survival (PFS), with log-rank tests used to compare groups. Cox proportional hazards models were used to explore the associations between nutritional status and survival outcomes, incorporating time-dependent covariates where applicable.

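### Only two-sample tests are named for a three-group comparison of continuous variables, and paired t tests are listed, with no pairing defined, for associations they do not test

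*Protocol*

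**What the plan says.** All of this is in the Protocol. The Nutritional assessments section divides the mPG-SGA score into "normal (0–2 points), mild malnutrition (3–6 points), and moderate malnutrition", the last starting at 7 points. That makes three ordered categories.

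The Statistical analysis plan section uses these categories as its example of a group comparison: "For group comparisons (e.g., normal vs. mild malnutrition vs. moderate malnutrition patients), independent t tests or Mann–Whitney U tests were used for continuous variables". For categorical variables it names chi-square and Fisher's exact tests, both of which accept three groups. It names no overall three-group test for continuous variables, no trend test and no rule for pairwise comparisons.

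For secondary analyses the same section plans to study "associations between nutritional status and psychosocial factors (e.g., EORTC QLQ-C30, HADS, PSQI) via paired t tests, mixed-effects models, and correlation analyses". The correlation is to be Spearman or Pearson according to distribution. The sentence does not say what forms a pair.

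Two other statements in the section bear on the weight of the point: "The primary outcome analysis will apply multivariate regression models, adjusting for age, sex, cancer stage", and "propensity score matching (PSM) will balance baseline differences between exposure groups". GEEs are planned for repeated measures and Cox models for survival.

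**The concern.** The issue is a mismatch between stated tests and stated questions, not missing detail.

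- **Three groups.** A t test or Mann–Whitney U test compares two samples. Applied to three categories, it yields up to three pairwise answers and no single answer on whether the categories differ. Unadjusted pairwise testing would also declare group differences more often than the nominal level.
- **Paired t tests.** The stated target is an association between nutritional status and a psychosocial score. A paired t test has a different null hypothesis, that the mean within-pair difference is zero. A significant result could be read as evidence on nutrition when it carries none.

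At stake are the unadjusted group comparisons of continuous variables and one set of secondary analyses. The latter serves a declared secondary objective: how nutritional health relates to psychological well-being and sleep.

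**Working it through.** **Inputs from the Protocol.** Three mPG-SGA categories; independent t or Mann–Whitney U tests for continuous variables; target N = 1,538. A two-sided α of 0.05 appears only in the Sample size section.

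**Assumed.** α = 0.05 for each pairwise test, no adjustment, and group splits, because the Protocol gives none.

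**The plan's own figure.** The Protocol gives no error rate for these comparisons, so there is none to reproduce. Its only derived figure is N, used here as the simulation size. With P1 = 0.50, P2 = 0.40 and unpooled variances:

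n per group = (1.960 + 0.842)² × (0.50×0.50 + 0.40×0.60) / 0.10² = 7.849 × 0.49 / 0.01 = 384.6

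Total with 50% attrition = 2 × 384.6 / 0.50 ≈ 1,538. This reproduces the target. (The rates written in words, 20% and 24%, do not reproduce it; that is a separate matter.)

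**Three pairwise tests: simple bounds.**
- Sum of the three levels: 3 × 0.05 = 15%.
- If the tests were independent: 1 − 0.95³ = 14.3%.

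The three comparisons share groups and are positively related, so the true figure is lower.

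**Simulation with no true difference, N = 1,538.** There were 100,000 runs per split for t tests and ANOVA, and 20,000 for the rank tests.

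| Split (normal / mild / moderate) | Any of 3 t tests | ANOVA | Any of 3 Mann–Whitney | Kruskal–Wallis |
|---|---|---|---|---|
| Equal | 12.2% | 5.0% | 12.1% | 5.1% |
| 60/30/10 | 11.8% | 5.1% | 11.8% | 4.8% |
| 20/40/40 | 12.1% | 4.9% | not run | not run |
| 80/15/5 | 11.6% | 4.9% | not run | not run |

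The result hardly depends on the assumed split. One overall test restores about 5%. If pairwise tests are kept alone, Bonferroni needs 0.05 / 3 = 0.0167 per pair.

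**Paired t test: what it tests.** The statistic is t = d̄ / (s_d / √n), where d is the within-pair difference, and the null is that d has mean zero. Take two unrelated scores in n = 769 patients (half of 1,538): one gamma with mean 2 × 2.0 = 4.0 and variance 2 × 2.0² = 8, the other gamma with mean 3 × 2.5 = 7.5 and variance 3 × 2.5² = 18.75. Then s_d = √26.75 = 5.17, the standard error is 5.17 / √769 = 0.187, and |t| ≈ 3.5 / 0.187 ≈ 18.7. In 2,000 simulated data sets the paired t test rejected in 100% and Spearman correlation in 5.0%. With no association at all, the paired t test responds only to the difference in means. The distributions are illustrative; the conclusion follows from the null hypothesis, not from these values.

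**The case against.** The strongest reply has four parts.

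1. **The three-group contrast is only an example, and real two-group contrasts exist**, such as NRS-2002 at or above 3 against below 3. The t and Mann–Whitney tests suit those. This stands, and they should be kept there. It does not rescue the sentence for the comparison it chooses to illustrate.
2. **Adjustment of pairwise tests is commonly left to a separate analysis plan, which is not shown here.** This stands: silence on adjustment is not the defect. A reader might infer that the error rate simply exceeds 5%. The Protocol does not say that. It fixes no α for these tests and does not call them unadjusted, so 12% is conditional. It also has no bearing on the paired t tests, whose problem is the hypothesis tested.
3. **The psychosocial question is not left without a valid method.** This stands. Mixed-effects models and correlations are in the same list, and GEEs are planned for quality of life. A reader might infer that the secondary objective cannot be met; the text does not support that. One method in a list of three does not fit.
4. **What is paired is unknown.** It could be two visits, two scores, or patients paired by the planned propensity score matching. For matched patients a paired test would compare exposure groups, but the Protocol draws no such link. This stands to the extent that the purpose is undefined rather than known to be wrong.

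Three further inferences are tempting but unsupported. That patients missing a visit would be dropped does not follow, since multiple imputation is planned and the follow-up section uses the last recorded assessment for those lost. That categories would be merged after the data are seen is suggested nowhere. That change over time would be reported as an association presumes a pairing by visit that the Protocol does not state.

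**Conclusion.** The concern holds in a limited form. For continuous variables the Protocol names only two-sample tests while giving a three-group comparison as its example, so no overall test of the three categories is specified. If all three pairs are tested at 0.05 without adjustment, the family-wise error is about 12% per variable against 5%. That figure rests on those two conditions and on assumed group splits, to which it is insensitive.

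Separately, paired t tests with no stated pairing are listed for associations that they do not measure, alongside two methods that do.

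A reader might infer that the study's main conclusions are at risk. They are not: primary inference rests on adjusted regression, with GEEs for repeated measures and Cox models for survival. The effect is confined to unadjusted group comparisons and one secondary analysis. The correction is still worth making, because the text names methods that do not fit and the remedy is nearly free.

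**What to change.** Change two sentences in the Statistical analysis plan section.

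1. **Group comparisons.** For continuous variables across the three mPG-SGA categories, name one-way ANOVA or Kruskal–Wallis, followed by Holm- or Bonferroni-adjusted pairwise contrasts. Keep independent t and Mann–Whitney tests for true two-group contrasts such as NRS-2002 at or above 3 against below 3. Leave chi-square and Fisher's exact tests as they are. A trend test across the ordered categories is an optional addition.
2. **Psychosocial associations.** Remove the paired t tests and rely on the mixed-effects model already listed, with nutritional category and visit as terms. Alternatively, keep the paired t test only for a stated within-patient change question, naming the two visits compared.

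The cost is two sentences of text. No new data, visits or patients are needed.
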